We designed the PACE clinical study initially to investigate platelet activity in PAD patients and the incidence of major adverse cardiac and limb events after lower extremity revascularization. PACE was set up to investigate the relationship between platelet activity and cardiovascular risk. Many studies suggest the overlapping nature of cardiovascular risk and dementia. Thus, we would like to extend findings that have established the link between heart disease and dementia to platelet activity and dementia. The comprehensive platelet characterization already performed would facilitate our study investigating the association between platelets and cognitive decline in this cohort of patients with established CVD. We will attempt to call all living participants and obtain telephone consent for the additional measure, assess vital status, and perform a validated survey of subclinical cognitive impairment in the PACE cohort with 2 previously validated neuropsychiatric tests that are frequently used in aging studies: TICS and Montreal Cognitive Assessment, MoCA. Both tests can be easily done remotely by trained personnel and are particularly good at detecting early subclinical impairment.

3. Specific Aims

Aim 1. To determine whether preoperative platelet activity measurements are independently associated with short-term cardiovascular events in PAD patients undergoing non-emergent lower extremity revascularization. We will characterize the platelet phenotype in 350 PAD patients before vascular surgery and use Cox proportional hazard models to determine the independent association of the platelet phenotype with risk of cardiovascular events in the first 30 days after surgery.

Aim 2. To determine whether postoperative platelet activity measurements are independently associated with long-term cardiovascular events in patients with established PAD. We will characterize the postoperative platelet phenotype following surgery and use Cox proportional hazards models to determine the independent association of the platelet phenotype with risk of long-term composite of myocardial infarction, stroke, or all-cause mortality with a mean follow-up of 2-years following vascular surgery.

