Blood samples will be assigned a unique code number and stored in the PI's lab without any identifying information other than a code number. The unique code number will not be based on any information that could be used to identify the subject (for example, social security number, initials, birth date, etc.). The master list linking names to code numbers will be kept in a locked file cabinet, separate from all research information placed under double lock and key at the PI's office at NYU Skirball 9th floor. All confidential data will be stored with a unique code as an identifier and will be protected by a double electronic lock. All physical data will be kept under double physical lock. Access to the data will be given to the study personnel only.

Samples will be stored for no more than 10 years following completions of the study. Samples will be used for testing other potential biomarkers in patient plasma and/or serum related to other endpoints not specified in the protocol (e.g. cancer, metabolic disease, etc.). Genetic testing will not be conducted on stored samples. Results of the future research will not be shared with the subjects or their study doctor, and will not become part of the medical records.

Subjects can request for withdrawal of samples at any time by contacting PI [name] in writing. His mailing address is [name]. Withdrawing

Authorization only affects uses and sharing of information after written request has been received, and subject may not withdraw his/her Authorization for uses or disclosures that have previously been made or must continue to complete analyses or report data from the research.

f. After Surgery and Follow Up

Starting on the day of surgery and continuing throughout hospitalization, a physician monitors the patient's course for clinically evident cardiovascular events (MI, stroke, TIA, major bleeding, kidney disease, or any surgical complication). Blood collections and/or ECG's that are performed as part of routine care and/or for study purposes will be recorded and may be used to help ascertain whether a cardiovascular and/or bleeding event has occurred. After hospital discharge, patients will be contacted by telephone (or during their routine clinical follow-up) at 30 days and every 6-month thereafter out to 5-years. At the patients' follow-ups they will be asked questions about their health, lifestyle, and medication use.

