3. Anemia (hemoglobin<8)
4. Any known hemorrhagic diathesis

Subjects will be re-enrolled and contacted the same way any subject is enrolled in the study. If the subject is undergoing a lower extremity revascularization procedure and they are referred to the study by a health care professional taking care of the subject, they will be approached by a member of the research team. This does not give a benefit to the patient other than to help answer an important scientific question. This poses no additional risk to the patient.

i. Endpoint Assessments

At every visit after randomization, the study coordinator will ask participants if they have had any symptoms or a report from a healthcare provider consistent with an endpoint event since the last study visit. If at any time the subject refuses to continue with follow-up, every attempt will be made to continue contact by written communication, email, by proxy contact with family, friends, or allied health care providers, or record review to determine if outcome events have occurred, unless the subject specifically refuses such follow-up. An independent clinical event adjudication committee (CEC) will review and adjudicate primary and selected secondary endpoint events in a blinded fashion based on study definitions.

5. Potential Risks and Benefits

The potential risks of performed phlebotomy are pain, bruising, fainting, or small infection at puncture site. The use of the blood for future sample storage and genetic testing raises special issues of confidentiality. Genetic testing can generate information about a subjects' personal health risks and can cause or increase anxiety, damage family relationships, and/or compromise insurability, employability and can even lead to discrimination. All confidential data will be stored with a unique code as an identifier and will be protected by a double electronic lock. All physical data will be kept under double physical lock. Access to the data will be given to the study personnel only thereby greatly reducing the possibility of psychological or social risks that could arise from knowledge of this genetic information, such as risk for employability or insurability or the risk of discrimination.

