Power and sample size analysis was performed to investigate appropriate sample size for evaluating platelet activity markers in subjects with cardiovascular disease CVD versus age- and sex matched controls. The study is powered based on the analysis of association between platelet activity and cardiovascular events. Based on published and preliminary data, we expect the 30-day event rate to be 22%. The relationship between platelet activity and short-term cardiovascular events will be assessed using 2 co-primary measures: LTA and MPA. Based on preliminary data, LTA levels have skewed distribution and MPA levels are normally distributed. Consider a transformation (e.g. log- or Box-Cox) on LTA measures that achieves Normality. With 200 participants, two-sided Wilcoxon test will have 80% power at the 0.025 significance level to detect an association between platelet reactivity and short-term events corresponding to a 0.5*standard deviation difference in platelet

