8.1 Data Analysis

All eligible subjects will be assigned a unique identification number upon enrollment in the study. Initial study data will be recorded on a printed form, which will be later converted to an IRB approved electronic database, REDCap. Only study personnel will have access to this database. All potential identifiers will be kept separately in a safe location at the PI's office in NYU Skirball 9th floor, where it will be placed under double lock and key and the PI will have access. After verification of entered data at completion of the study all potential identifiers will be stripped from the database.

Descriptive statistics, including frequency tables, measures of center and variability, and graphical displays will present baseline subject characteristics. Similar analyses will present values of platelet activity measures.

Primary Platelet Activity Measures: LTA and MPA To test the hypothesis that platelet activity measurements are independently associated with 30-day (Aim 1) and long-term (Aim 2) cardiovascular events in patients undergoing lower extremity revascularization we will employ the following analysis. For Aim 1, platelet activity will be measured preoperatively and the main outcome will be 30-day cardiovascular events. For Aim 2, platelet activity will be measured 48 hours postoperatively and the main outcome will be long-term (mean follow-up ~ 2 years) cardiovascular events. We will perform univariate analysis to investigate the association between LTA and MPA platelet activity measures and cardiovascular events. Next, we will examine differences in sociodemographic/clinical factors between participants with and without a cardiovascular event using two-sided tests of proportions for categorical variables (chi-square, Fisher's exact) and t-tests or non-parametric alternatives (e.g., Wilcoxon test) for continuous measures.

The analysis plan outlined above for the primary platelet activity measures will be applied to the set of secondary measures including thrombin. In addition, the analysis plan outlined above for the primary outcome measures will be applied to the secondary outcome measures including major bleeding.

To identify novel mRNA-miRNA target pairs involved in platelet activation, we will computationally inversely correlate miRNA expression with expression of gene targets using established prediction databases

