8.2 Data Safety Monitoring Plan

There are no primary or secondary endpoints. Patients undergoing vascular surgery as part of their routine clinical care will have a blood collection before and after surgery to help identify future markers in their blood related to clotting and bleeding episodes. The proposal is deemed to be low risk for subjects. Safety information will be collected via telephone at 30 days after the surgery, case report form, and/or scheduled follow-up visits as part of standard of care.

PI will conduct interim monitoring of accumulated data from research activities to assure the continuing safety of participants, relevance of the study question, appropriateness of the study, protocol compliance and integrity of the accumulating data. The PI in conjunction with NYU IRB will be responsible for monitoring the data and conducting safety reviews at a minimum of every 12 months when annual re-approval is sought. Any unanticipated serious adverse event will be reported to IRB within 72 hours. During the review process, the PI and NYU IRB will evaluate whether the study should continue unchanged, require modification/amendment, or close to enrollment.

9. Confidentiality:

Study is for research purposes only. Individual result will not be given back to study participant. This will include information from final results of the study, interim results of the study and incidental findings. Research result will never occur in medical records. Confidentiality will be preserved to the fullest extent by the research team. All data will be stored with a unique code that does not identify the subject. Furthermore, data will be saved using a double electronic lock. All physical data will also be kept under double physical lock. Access to the data will be given to the study personnel only.

10. Appendix A: Schedule of study related procedure

	Pre-op Period	POD 2 (+/- 1 day)	Discharge	Post-op Appointment follow-up	Long-term follow-up
Eligibility	X				
Informed consent	X				
Demographics	X				
Medical history/status	X	X	X	X	X
Medication use	X	X	X	X	X
Vital signs	X	X	X		
Standard lab results	X	X	X	X	X
Troponin	X	X			

ECG	X	X			
Blood draw	X	X		X	
Urine sample	X			X	
Endothelial dysfunction assessment	X	X		X	
QOL assessment	X			X	X
Diet questionnaire	X				
Lifestyle assessment	X			X	X
Medication adherence	X			X	X
Hospitalization assessment			X	X	X
Endpoint assessment		X	X	X	X
Cognitive Function Test					X

1. Pre-operative period

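### The 30-day outcome of Aim 1 has no stated components, and the texts bearing on it disagree about bleeding, death and whether the study has endpoints

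*Combined protocol and SAP*

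**What the plan says.** Aim 1 (Section 3) sets out to estimate the "independent association of the platelet phenotype with risk of cardiovascular events in the first 30 days after surgery". Section 8.1 repeats that label for the main outcome of Aim 1. Neither place lists components.

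Section 4.f says that from the day of surgery through hospitalization a physician watches for cardiovascular events, which it spells out as "MI, stroke, TIA, major bleeding, kidney disease, or any surgical complication". Death is not in that list. The next sentence of 4.f names cardiovascular and bleeding events as two separate things.

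Aim 2 has its own list, the "long-term composite of myocardial infarction, stroke, or all-cause mortality", and ties it to a mean follow-up of 2 years.

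Section 8.1 says that the primary analysis plan "will be applied to the secondary outcome measures including major bleeding".

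Section 4.i says that an independent committee "will review and adjudicate primary and selected secondary endpoint events" using study definitions, which the available text does not give. Section 8.2 opens with "There are no primary or secondary endpoints".

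Section 8 bases power on an expected 30-day event rate of 22%, drawn from published and preliminary data, without saying which events make up the 22%.

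**The concern.** The footnote to the inclusion criteria (Section 4.g) describes peri-procedural events as the study's major aim, so the outcome left undefined is the one that matters most.

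If an analyst filled the gap with the Section 4.f list, three things would follow. A major bleed would count in both the primary outcome and a secondary one. Any surgical complication would count as a cardiovascular event. A death not accompanied by a listed event would not count: it would be censored in the Aim 1 Cox model and would fall in the event-free group of the Wilcoxon comparison.

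Section 4.d contrasts clotting with bleeding as different phenotypes. Pooling them, together with complications that may have nothing to do with platelets, could dilute the association Aim 1 is meant to detect. Leaving the composite open also allows it to be chosen after platelet results and events are known. Finally, the 22% cannot be checked, or replaced by a better estimate, until the events it covers are named.

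**Working it through.** **1. The texts side by side**

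| Place | Bleeding | Death | Applies to |
|---|---|---|---|
| Aim 1; 8.1 main outcome | not stated | not stated | 30 days |
| 4.f list | inside cardiovascular events | absent | hospital stay |
| 4.f next sentence | separate from cardiovascular events | not stated | event ascertainment |
| Aim 2 | absent | included, all causes | long term |
| 8.1 secondary outcomes | separate, secondary | not stated | no window given |
| 4.i | primary and secondary endpoints adjudicated | not stated | all follow-up |
| 8.2 | says there are no endpoints | – | – |

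No row assigns components to the 30-day outcome. The 4.f list conflicts with its own next sentence and with 8.1. Section 8.2 conflicts with 4.i and 8.1.

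**2. The plan's own power figure**

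Inputs from Section 8: N = 200, event rate 22% (44 with an event, 156 without), difference d = 0.5 SD, two-sided level 0.025 (z = 2.241), Wilcoxon test. Its efficiency relative to the t-test on normal data is 3/π = 0.955.

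Power = Φ( d × √(0.955 × n1 × n0 / N) − z )

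- n1 × n0 / N = 44 × 156 / 200 = 34.32
- 0.5 × √(0.955 × 34.32) = 2.862
- Φ(2.862 − 2.241) = Φ(0.621) = **73%**

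Without the efficiency factor the result is 75%. A simulated rank test (20,000 runs) gives 72%. The stated 80% is approached only at two-sided 0.05, where z = 1.960 and Φ(0.902) = 82%. This gap has nothing to do with the event list, but it has to be put right when the power is restated.

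**3. Dependence on the rate, at the planned enrolment of 350**

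The 15% and 10% rates are assumptions for a narrower composite; the documents give none.

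| Rate | Events | n1 × n0 / N | Power |
|---|---|---|---|
| 22% | 77 | 60.06 | Φ(3.787 − 2.241) = 94% |
| 15% | 52.5 | 44.63 | Φ(3.264 − 2.241) = 85% |
| 10% | 35 | 31.50 | Φ(2.742 − 2.241) = 69% |

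The rate needed for 80% power is about 13% with 350 participants and about 27% with 200.

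**4. Dilution, as illustration only**

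Suppose that 0.5 SD applies to thrombotic events alone and that a fraction f of counted events does not follow it. The average difference becomes 0.5(1 − f) if those events are unrelated to platelet activity, and 0.5(1 − 2f) if they run the opposite way. At N = 350 and 22%, starting from 94%:

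- f = 25%, unrelated: 0.375 SD, power 73%
- f = 40%, unrelated: 0.30 SD, power 51%
- f = 25%, opposite: 0.25 SD, power 36%

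Neither the fractions nor the assignment of 0.5 SD to thrombotic events comes from the documents.

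**The case against.** A reader might infer that 4.f is the protocol's only event list and that Aim 1 therefore does pool bleeds with thrombotic events. The documents do not support this. Aim 2 gives a second list. The 4.f list is in-hospital surveillance, is not called an endpoint and does not cover the full 30 days. Section 8.1 makes major bleeding secondary, and 4.d as well as the next sentence of 4.f keep bleeding apart. The weight of the text is against bleeding being in the primary outcome. This stands: pooling is a possibility left open, not a stated plan.

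The dilution figures also rest on a choice. Section 8 gives 0.5 SD for the short-term events it powered, whatever those were. If that value already describes the full composite, no further dilution applies. This stands too, so the figures show a mechanism and do not estimate a loss.

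Definitions may exist elsewhere. Section 4.i refers to study definitions, 4.b to an attached case report form that is not shown, the power paragraph breaks off mid-sentence, and part of the document was not available. The 8.2 sentence sits in a safety-monitoring section and may be loose wording. These points limit any claim that no definition was ever written. They do not remove the conflicts in the text at hand.

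A reader might also infer that Aim 2's composite was meant for 30 days, or that it underlies the 22%. Nothing says so. The background before Section 3 speaks of major adverse cardiac and limb events, which neither list covers.

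**Conclusion.** The concern holds as under-specification of the main outcome, with internal conflict. The available text never itemises the 30-day outcome. The nearest list treats bleeding and death differently from 8.1 and Aim 2, and 8.2 contradicts 4.i and 8.1. Read literally, the 4.f list would count bleeds twice and miss some early deaths; the documents show that this could happen, not that it is intended. The effect on the association cannot be sized without component rates.

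What can be sized is the dependence on the unexplained 22%. At 350 participants the study keeps at least 80% power down to a rate of about 13%, and falls to 69% at 10%. At the 200 participants in the power statement it has about 73% even at 22%. These figures assume normal data, a 0.5 SD difference and two-sided 0.025.

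**What to change.** - **Aim 1 and 8.1:** state the components of the 30-day outcome as intended when the study was designed, count all-cause death as an event as Aim 2 does, and say whether TIA and limb events count. Platelet phenotypes are described as already measured, so record when the definition was fixed and whether outcome data had been seen by then.
- **4.f:** separate major bleeding, kidney disease and surgical complications from cardiovascular events. Analyse major bleeding as the secondary outcome 8.1 already names.
- **Section 8:** say which composite the 22% describes and where it comes from. Restate the expected rate and power for the composite used, at the planned enrolment, and correct the 80% at N = 200.
- **8.2:** reword the opening sentence to agree with 4.i and 8.1.
- **4.i:** include the study definitions or point to where they are kept.

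The cost is mainly wording and one recalculation. Whether every component has been adjudicated cannot be told from the documents: 4.i covers primary and selected secondary events, so some review of existing records may be needed. The downside is that the restated rate and power may be less favourable than 22% and 80%.

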5.1 Benefits

The proposed study will examine a panel of markers related to platelet function, inflammation, and coagulation and assess their ability to predict cardiovascular events following vascular surgery. The long-term goal is to develop a clinically useful assessment of platelet activity for risk stratification that may ultimately serve as a target for therapeutic intervention. The platform proposed will serve as a basis for future research and intervention, and hopefully, will have a great impact on subjects undergoing vascular surgery. There might be no direct benefit to enrolled subjects. The cognitive function follow-up screening will act as another clinically valuable measure of risk predicted by platelet activity. We aim to use the information as future clinical research goal and will not provide direct benefit to patients.

6. Cost

There is no cost or compensation to the study participants. There is also no direct benefit expected from the participation in this study. This study will provide potentially valuable information with minimal risk to study subjects. It is hoped that knowledge gained will be of benefit to others in the future.

7. Screening Log

During the study enrollment period, sites may collect de-identified data on all patients undergoing lower extremity revascularization. The goal of this effort will be to describe the characteristics of patients who are screened but not enrolled and to document the major reasons for exclusion. Examples of data elements to be collected, when available, include: (age [recorded for patients <90 years of age, recorded as 90 if >90 years of age], sex, race/ethnicity, basic medical history from medical chart (if available), in-hospital events (if available from the chart) and, if excluded from the study, reason(s) for exclusion will be recorded). Importantly, only de-identified health information will be recorded and stored in the PI's office at NYU Skirball 9th floor, under double physical lock and key.

8. Statistical Analysis

Power and sample size analysis was performed to investigate appropriate sample size for evaluating platelet activity markers in subjects with cardiovascular disease CVD versus age- and sex matched controls. The study is powered based on the analysis of association between platelet activity and cardiovascular events. Based on published and preliminary data, we expect the 30-day event rate to be 22%. The relationship between platelet activity and short-term cardiovascular events will be assessed using 2 co-primary measures: LTA and MPA. Based on preliminary data, LTA levels have skewed distribution and MPA levels are normally distributed. Consider a transformation (e.g. log- or Box-Cox) on LTA measures that achieves Normality. With 200 participants, two-sided Wilcoxon test will have 80% power at the 0.025 significance level to detect an association between platelet reactivity and short-term events corresponding to a 0.5*standard deviation difference in platelet

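### The stated 80% Wilcoxon power with 200 participants at two-sided 0.025 is about 71–73% for a Normal-scale marker

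*Combined protocol and SAP*

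**What the plan says.** The power statement is in Section 8 (Statistical Analysis), in the paragraph before 8.1. It gives these inputs:

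- Event rate: "we expect the 30-day event rate to be 22" per cent.
- Markers: the relationship with short-term events "will be assessed using 2 co-primary measures: LTA and MPA".
- Distributions: "LTA levels have skewed distribution and MPA levels are normally distributed". The plan then suggests considering a transformation "on LTA measures that achieves Normality".
- Sample size, test, level and power: "With 200 participants, two-sided Wilcoxon test will have 80% power at the 0.025 significance level to detect an association between platelet reactivity".
- Effect size: "corresponding to a 0.5*standard deviation difference in platelet". The readable text breaks off here, and nothing below relies on what follows.

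Section 8.1 defines the comparison for Aim 1: "For Aim 1, platelet activity will be measured preoperatively and the main outcome will be 30-day cardiovascular events". Section 3 (Aim 1) gives a different number of participants from the power statement: "We will characterize the platelet phenotype in 350 PAD patients before vascular surgery". Section 4a also gives a recruitment target of 350.

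**The concern.** The sample size, event rate, effect size, test and significance level are all given, so the power can be recomputed directly. The two groups are very unequal (22% against 78%), and 0.025 is a stricter level than 0.05. Together these make 80% look high for 200 participants.

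This sentence is the power claim for Aim 1. If it is wrong, a reader is told that the chance of missing a half-SD difference in a given marker is 20% when it is nearer 28%. The error could lie in the power, the level or the sample size, and the text does not show which. The readable text gives no power figure for the 350 participants actually planned.

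**Working it through.** **Inputs (Section 8).** N = 200. Event rate 22%, so n₁ = 0.22 × 200 = 44 with an event and n₂ = 156 without. Difference 0.5 SD, read as the shift between these two groups in within-group SD units. Two-sided level 0.025, so the critical value is z(0.9875) = 2.241. The marker is Normal: MPA as stated, or LTA after a successful transformation.

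**Trying to reproduce 80% at the stated level**

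1. *Normal approximation with the Wilcoxon efficiency 3/π.*
   - Standardised effect: 0.5 / √(1/44 + 1/156) = 2.929.
   - Times √(3/π): 2.862.
   - Power = Φ(2.862 − 2.241) = Φ(0.621) = **73.3%**.
2. *Noether's formula.*
   - P(X > Y) = Φ(0.5/√2) = 0.638.
   - √(12 × 0.22 × 0.78 × 200) × (0.638 − 0.5) − 2.241, with P unrounded, gives a power of **71.3%**.
3. *Simulation of the rank-sum test* (Normal shift, 40,000 datasets per run): **71.8% to 72.5%** over several runs.
4. *Two-sample t-test*, which is the more efficient test for Normal data: 74.8%.

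None of these gives 80%.

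**What would give 80%?**

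| Change to one input | Result |
|---|---|
| Two-sided level 0.05 | 80.1% (Noether), 81.7% (efficiency), about 81% (simulation) |
| Level giving exactly 80% at N = 200 | 0.0497 (Noether), 0.0433 (efficiency) |
| N for 80% at 0.025 | 241.8 (Noether), 232.0 (efficiency) |
| N for 80% at 0.05 | 199.7 (Noether), 191.6 (efficiency) |
| Difference for 80% at N = 200, level 0.025 | 0.552 SD (Noether), 0.539 SD (efficiency) |
| Equal groups, 100 vs 100, level 0.025 | 88.8% (efficiency) |

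Noether's sample size at two-sided 0.05 is 199.7, almost exactly the stated 200. That fits a calculation done at 0.05, but the documents do not show the calculation.

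**Sensitivity to how the inputs are read (level 0.025, N = 200)**

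- Event count varying as Binomial(200, 0.22): 70.8% (Noether) to 72.7% (efficiency).
- SD read as the overall SD. The within-group shift becomes 0.5 / √(1 − 0.22 × 0.78 × 0.25) = 0.511, and power is 73.3% to 75.3%.
- Untransformed LTA, taken as lognormal with an upward shift of 0.5 raw-scale SD: 73% at log-SD 0.10 (skewness 0.30), 80% at log-SD 0.28 (skewness 0.88), 93% at log-SD 0.50 (skewness 1.75). The documents give no skewness for LTA, so this is a range.

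**At the planned 350** (77 vs 273), level 0.025: 92.9% (Noether), 93.9% (efficiency), 93.6% (simulation). The difference detectable with 80% power is 0.41 SD.

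**The case against.** The strongest objection is that the sentence does not say the 80% is per marker. It follows the naming of two co-primary markers and uses 0.025, which looks like 0.05 divided by two. Read as the power to detect at least one marker, with 0.5 SD in both, the figure depends on their correlation: about 92–93% at 0, 85–87% at 0.5, 80–82% at 0.8 and 77–79% at 0.9. So about 80% is attainable on this reading if the markers are highly correlated. However, the sentence describes a single Wilcoxon test and mentions neither a correlation nor power for at least one success. This reading cannot be excluded, but the text does not support it. What stands is that the corrected sentence should say the figure is per marker.

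Second, distribution matters. Skewed LTA can reach 80%, and a logistic shape comes close (79.6% by efficiency, 78.2% simulated). The transformation of LTA is only to be considered, not fixed. This stands for LTA. It does not help MPA, which the plan calls Normal.

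Third, the practical effect is small. Enrolment is 350, and the aims call for Cox models of independent association, to which an unadjusted Wilcoxon figure is only an approximation. This stands and limits the weight of the point. The sentence nevertheless ties 80% to 200 participants, and that figure is wrong.

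Fourth, the inference that 0.05 was used is unproven. That is accepted, and the conclusion does not depend on it.

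**Conclusion.** The concern holds. For a Normal-scale marker, 200 participants with 22% events and a 0.5 SD difference give a two-sided Wilcoxon test at 0.025 a power of about 71–73%, not 80%. The shortfall of 7 to 9 points exceeds any difference between formulas, and even the t-test falls short.

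The conclusion assumes that the groups are participants with and without a 30-day event, that the 0.5 SD is the difference between them, and that power is meant per marker. It makes no claim about untransformed LTA, for which 80% may be right. No allowance was made for missing assays or loss to follow-up, which would lower the power. This is a wrong figure in the text, not a design flaw.

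**What to change.** Rewrite the power sentence so that sample size, level, power and scale agree, and state that the figure is per marker. Either of these would do:

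- **Keep 200.**

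  > *With 200 participants and a 22% event rate (44 vs 156), a two-sided Wilcoxon test at 0.025 has about 72% power per marker for a 0.5 SD difference on a Normal scale, and 80% power for about 0.54–0.55 SD.*

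- **Use the planned enrolment.**

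  > *With 350 independent, evaluable participants (77 vs 273), the unadjusted two-sided Wilcoxon test at 0.025 has about 93% power per marker for a 0.5 SD difference on a Normal scale, and 80% power for about 0.41 SD.*

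The second version needs its qualifiers. Section 4g allows re-enrolment for another procedure more than 90 days after the first, so 350 enrolments need not be 350 independent people, and the documents give no evaluable fraction.

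If the authors find that the 80% was computed at two-sided 0.05, they should correct the level and also report the 0.025 figure, because there are two co-primary markers. If they meant power for at least one marker, they should say so and give the assumed correlation.

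The cost is one sentence, with no extra participants and no change to design or analysis. If 200 and 0.025 are both kept, the stated power becomes less favourable.
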